### Sponsor-Investigator Reporting Procedures

The Sponsor-Investigator must assess and categorise the Expedited Safety Reports received from Investigators and report these to all Site Principal Investigators, the approving HREC and TGA in accordance with the NHMRC's 'Safety monitoring and reporting in clinical trials involving therapeutic goods' (November 2016) and any additional requirements of the approving HREC. All safety reports must clarify the impact of the safety event on participant safety, trial conduct and trial documentation.

The Sponsor-Investigator is responsible for the following reporting to PIs, the HREC(s) and TGA:

1. All SSIs that meet the definition of a USM within 72 hours of becoming aware of the issue.
2. All other SSIs within 15 calendar days of instigating or becoming aware of the issue
3. For SSIs leading to an amendment of trial documentation:
  - a. Submit details of the SSI without undue delay and no later than 15 calendar days of becoming aware of the issue.
  - b. Submit amendment to the HREC without undue delay.
4. For SSIs leading to temporary halt or early termination of a trial for safety reasons:
  - a. Communicate reasons, scope of halt, measures taken, further actions planned without undue delay and no later than 15 calendar days of decision to halt.
  - b. For a temporary halt, notify the PIs, HREC and TGA when the trial restarts, including evidence that it is safe to do so.

The Sponsor will also report SUSARs to the TGA as follows:

1. Fatal or life-threatening SUSARs immediately, but no later than 7 calendar days after being made aware of the issue (follow up info within a further 8 calendar days)
2. All other SUSARs no later than 15 calendar days of being made aware of the issue

The Sponsor is responsible for providing the additional safety information to the approving HREC:

1. Provide an annual safety report, including a summary of the evolving safety profile of the trial
2. Provide any updated Product Information/Investigator's Brochure for the investigational products (if applicable)

---

The Sponsor is also responsible for providing any updated Product Information/Investigator's Brochure to Investigators.

## **7 DATA MANAGEMENT**

### **9.1 Overview**

The investigators are responsible for ensuring the accuracy, completeness, legibility, and timeliness of the data reported. All source documents should be completed in a neat, legible manner to ensure accurate interpretation of data. The investigators will maintain adequate case histories of trial participants, including accurate case report forms (CRFs), and source documentation. The Investigators must use maintain a record that details the location of essential documents, including those documents stored outside the Investigator Site File. Consider locations of all source documents, e.g. pharmacy, pathology, radiology, Investigator's office.

### **9.2 Data Collection, processing and storage**

#### **9.2.1 Source Data**

Outcome data will be recorded in online database RedCap through Monash University, and notes made in the patient's electronic medical record. Data analysis will be performed using patient hospital numbers only, and additional information about the data (such as notes about study write-up and thesis drafts) will be stored on locked laptop.

Patient consent forms will be stored in a locked office in the department of surgery, Frankston Hospital.

Study investigators will enter the data directly into RedCap and make a note in the patient's electronic medical record that this has been performed.

#### **9.2.2 Data Capture Methods and Storage**

Study investigators will be briefed on how to record information in their assessment and consultation notes for the trial as per the protocol using RedCap. Education material and training on the use of RedCap will be provided by the Principal Investigator.

Clinicians will document the following assessment criteria in RedCap at each two week, six week, twelve week and twenty-six week follow up point:

---

A: Does the patient report a history of:

- sensory changes (hyperaesthesia and/or allodynia)
- vasomotor changes (temperature asymmetry, skin colour changes and/or skin colour asymmetry)
- sudomotor/oedema changes (oedema, sweating change or sweating asymmetry)
- motor/trophic changes (decreased range of motion and/or motor dysfunction and/or weakness/tremor/dystonia and/or trophic changes of hair/nails/skin?)

---

B: Does the clinician observe:

- sensory changes (hyperaesthesia and/or allodynia)
- vasomotor changes (temperature asymmetry, skin colour changes and/or skin colour asymmetry)
- sudomotor/oedema changes (oedema, sweating change or sweating asymmetry)
- motor/trophic changes (decreased range of motion and/or motor dysfunction and/or weakness/tremor/dystonia and/or trophic changes of hair/nails/skin?)

---

C: Is there another diagnosis that better explains the signs and symptoms during today's history and examination?

Yes  
 No

---

D: Is the patient's pain disproportionate to the inciting event?

Yes  
 No

---

If the patient responds yes to three out of four questions in part A, AND the clinician observes two out of four signs in part B, AND answers yes to C and D, the patient meets the criteria for CRPS diagnosis.

Yes  
 No

Does the patient meet the criteria for CRPS diagnosis?

---

How has the patient felt since their last visit? (eg. fine, unwell, nauseated, in pain)

\_\_\_\_\_

---

Has the patient had any side effects to the medication such as abdominal upset, back pain, nausea or vomiting?

Yes  
 No

---

Has the patient taken the medication as prescribed?

Yes  
 No

The diagnosis of CRPS will be made if the patient meets the Budapest criteria, and patients will be referred to physiotherapy for pain management. The investigator will record whether the patients was diagnosed with CRPS in the EMR and communicate this back to the patient's General Practitioner via a clinical letter (this is standard practice in the event of a post-operative complication).

Randomisation data will be stored on a locked computer in the Department of Surgery.

Data analysis will be performed using non-identifiable hospital UR numbers only, stored on a locked laptop by the senior researcher and in a password protected file and using RedCap.

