## 3.2 Outcomes

**Table listing objectives and outcomes**

OBJECTIVE	OUTCOME & OUTCOME MEASURE
Primary	
Primary objective – to determine if the proposed protocol is feasible with regards to: 
 
• Recruitment capability
 
• Data collection procedure
 
• Suitability of intervention
 
• Resource availability
 
• Participant response
 
	Recruitment capability: 
 
• Successful recruitment of pre-determined patient numbers
 
 Data collection procedure: 
 
• Successful follow up at established time-points
 
• Qualitative clinical feedback about ease of assessment/data collection
 
• Lost to follow up rate
 
 Suitability of intervention: 
 
• Patient-reported compliance with medication
 
• Patient-reported complication
 
• Qualitative assessment of patient feedback
 
 Resource availability 
 
• Establishing paid and unpaid labour costs required for the trial
 
• Availability of medication and placebo
 
 Participant response: 
 
• Qualitative participant feedback
 
• Participant engagement/follow up
 

Secondary	

 
1. To determine if vitamin C prevents CRPS in patients with lower limb extremity trauma in a dose-response manner
 
2. to determine the incidence of CRPS in lower limb extremity trauma
 
	To determine if vitamin C prevents CRPS in patients with lower limb extremity trauma in a dose-response manner: Patients are evaluated at four points post-operatively: 
 
• 10-14 days
 
• 5-6 weeks
 
• 10-12 weeks
 
• 26 weeks
 
 The outcome of a positive diagnosis for CRPS will be made if the patient meets the 'Budapest criteria' at any of their four post-operative review appointments. This is a combination of asking patients about their symptoms and

OBJECTIVE	OUTCOME & OUTCOME MEASURE

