### 5.2.4 Storage, preparation, dispensing and administration of trial drug

The five sites will be allocated a box of medication from Peninsula Health pharmacy. This will be kept in a locked office with access only by the primary researcher at that site. Whilst on-site at Peninsula Health, this medication will be stored in pharmacy.

---

Patients will be educated on the dosage, timing and frequency of the medication and will be advised to take the capsules until the box is finished (50 days). Medication is self-administered.

In the setting of delayed or missed doses, patients will be told not to “make up” the dose but instead continue their normal daily dosing.

Patients will be asked at their review whether they have adhered to the medication schedule, if they had any problems with taking the medication or if any side effects such as gastrointestinal upset had occurred.

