#### **5.2.6 Measurement of participant adherence**

Patients will be asked at their two-week, six-week, twelve-week and twenty-six week reviews whether they had been adherent with taking their medication. Adherence will be recorded in the medical record. If patients miss more than three doses at any stage in the preceding two weeks, they will be deemed non-adherent to the treatment protocol and participation withdrawn. Data up to that point will be analysed in the groups to which they were randomised following the intention-to-treat principle, but adherence will be noted and documented.

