All hospital registrars and orthopaedic consultants will be given a verbal presentation to introduce the research project and the study investigators involved in the trial. This will be done at an orthopaedic weekly business meeting for approximately one hour. Education on trial design and CRPS examination and history will be provided. Study researchers will conduct follow-up history and examination.

Assessment at two weeks, six weeks, twelve weeks and twenty-six weeks is standard treatment for most bony and soft tissue injuries of the lower limb and does not deviate from normal procedure.

If a patient is diagnosed with CRPS, they will be referred to physiotherapy as per usual care. The method for which they are referred will depend on whether the patient is referred in the public or private systems:

- Public: a written referral will be made to the Physiotherapy Department at Peninsula Health. This is standard practice for a patient diagnosed with CRPS in this institution.
- Private: a written referral will be made to the patient's regular physiotherapist. If the patient does not have a regular physiotherapist, a choice of local, experienced physiotherapists will be offered for a referral and a written referral will be made. This is standard practice for management of CRPS in this system.

Patients will also be asked at each review appointment if they have adhered with the medication and if they are experiencing any side effects.

---

How has the patient felt since their last visit? (eg. fine, unwell, nauseated, in pain)

\_\_\_\_\_

---

Has the patient had any side effects to the medication such as abdominal upset, back pain, nausea or vomiting?

Yes  
 No

---

Has the patient taken the medication as prescribed?

Yes  
 No

If patients have skipped up to three consecutive dose of their medication, they will be

---

deemed 'non adherent and a note will be made on their Electronic Medical Record but will still be analysed to where they were randomised. If patients skip one dose they will be advised to simply continue the medication and not 'make up' a dose.

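### The only structured patient-reported adherence item shown is an undefined Yes/No, which on its own cannot yield either of the protocol's two non-adherence rules

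*Protocol*

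**What the plan says.** The table in Protocol section 3.2 lists "Patient-reported compliance with medication" under suitability of the intervention, part of the primary feasibility objective. It gives no threshold, no scoring rule and no source field.

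Section 9.2.2 prints the RedCap form and fixes when it is completed: "Clinicians will document the following assessment criteria in RedCap at each two week, six week, twelve week and twenty-six week follow up point". Its adherence item is "Has the patient taken the medication as prescribed", with Yes and No as the only answers. Section 7.4 shows the same item.

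Two rules define non-adherence:

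- Section 5.2.6: "If patients miss more than three doses at any stage in the preceding two weeks, they will be deemed non-adherent to the treatment protocol". The same section attaches withdrawal of participation to this label and says: "Adherence will be recorded in the medical record".
- Section 7.4: "If patients have skipped up to three consecutive dose of their medication, they will be" labelled non-adherent, with a note in the electronic medical record and analysis still in the randomised group.

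On missed doses, section 5.2.4 says "patients will be told not to “make up” the dose but instead continue their normal daily dosing". Section 5.2.5 adds the return of leftover capsules after day 50, recorded reasons for departing from the regimen, and a final reconciliation of drug dispensed, consumed and returned.

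**The concern.** Both rules need information that a Yes/No answer does not carry: a number of missed doses within a two-week window, or the length of a run of skipped doses. The answer itself is also undefined. Read strictly, one missed capsule in a once-daily regimen makes it No. Read leniently, a patient who missed doses and then followed the section 5.2.4 advice has kept to instructions and could fairly be ticked Yes. The form does not choose between these readings. It is completed at five sites, and section 7.4 expects junior doctors to rotate through.

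At stake is a descriptive compliance figure that is meant to inform a later definitive trial. A separate analysis plan could set a threshold, but it could not recover a count that was never collected, and section 11.2.1 rules out data substitutions for adherence. Section 5.2.6 also ties a trial consequence to the count, and the form could not show whether that rule had been applied evenly.

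**Working it through.** The protocol gives no compliance target and no adherence figure, so there is nothing of its own to reproduce. The check sets the texts side by side and then adds an illustration.

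**1. Three patterns of missed doses within 14 dosing days**

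| Pattern | Form, strict | Form, lenient | Rule in 5.2.6 | Rule in 7.4 |
|---|---|---|---|---|
| A: one missed | No | Yes | adherent | unclear (a run of one) |
| B: three missed in a row | No | Yes possible | adherent | non-adherent |
| C: four missed, none consecutive | No | Yes possible | non-adherent | unclear (runs of one only) |

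The strict form gives the same answer for A, B and C. The lenient form may also give the same answer for all three. Section 5.2.6 separates C from A and B, and section 7.4 clearly labels only B. So the form cannot yield either rule, and the two rules do not agree on B.

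**2. What the other sources add**

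- Medical record (5.2.6, 7.4): adherence is noted, but no count or timing is specified.
- Capsule return and reconciliation (5.2.5): one total per participant over 50 days. It cannot place misses in a two-week window or show whether they were consecutive, and it is not patient-reported.

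**3. When a two-week look-back can apply**

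Dosing lasts 50 / 7 = 7.1 weeks. The preceding two weeks are days 84 − 14 = 70 to 84 at the twelve-week review, and days 182 − 14 = 168 to 182 at the twenty-six-week review. Neither window normally contains a dosing day. The 5.2.6 rule can therefore be applied at the first two reviews only, covering at most 2 × 14 = 28 of the 50 dosing days. The first window will often be shorter: the synopsis allows that review from day 7, and dosing may start up to 72 hours after surgery.

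**4. Illustration**

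Assume that doses are missed independently with daily probability p over 14 doses. Neither the independence nor any value of p comes from the protocol.

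- None missed (strict reading of the form): (1 − p)^14
- At most three missed (5.2.6): sum over k = 0 to 3 of C(14, k) p^k (1 − p)^(14 − k)

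For p = 0.05 the first is 0.95^14 = 0.488. The second is 0.488 + 0.359 + 0.123 + 0.026 = 0.996.

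| p | None missed | At most three missed | Gap (points) |
|---|---|---|---|
| 0.02 | 75% | >99.9% | about 25 |
| 0.05 | 49% | 99.6% | about 51 |
| 0.10 | 23% | 95.6% | about 73 |

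These gaps apply only if every clinician ticks No after a single miss.

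**The case against.** A reader might infer that the primary compliance measure is scored on a different threshold from the protocol's own rule. The document does not support that. Section 3.2 sets no threshold and ties the measure neither to the Yes/No item nor to 5.2.6, and with two conflicting rules there is no single rule to depart from. How a descriptive measure is derived may properly be left to an analysis plan.

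A reader might also infer that non-adherence could not be established from any trial data. That goes too far. Section 5.2.6 sends adherence to the medical record, section 9.2.1 provides for record notes alongside RedCap, and section 5.2.5 yields a 50-day capsule total. A clinician could ask about missed doses, apply a rule at the visit and note the result. The list in 9.2.2 is also not said to be the whole case report form. What remains is that no count is specified in any of these places.

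It would be tempting to present 49% against 99.6% as the compliance figure at risk. That contrast depends on an assumed miss rate, on independence, on a fully dosed 14-day window and on the strict reading of the question. On the lenient reading it shrinks or disappears.

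Finally, the consequences are limited. Section 11.2 analyses all randomised participants regardless of adherence, and section 11.3 specifies no adherence-based analysis. This stands, and it makes the point a data-capture improvement with no bearing on the treatment comparison.

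**Conclusion.** The point holds in a limited form. The one structured patient-reported adherence item shown is an undefined Yes/No. On its own it yields neither the count rule in 5.2.6 nor the consecutive-dose rule in 7.4, and the other sources are not specified in a way that fills the gap. This follows from the text and needs no assumption about adherence.

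Its numerical size cannot be derived from the protocol. In the illustration, the share with no missed dose and the share with at most three differ by about 25 to 73 percentage points for assumed daily miss rates of 2% to 10%. That shows only that the choice of definition can matter a great deal. What is affected is a descriptive feasibility figure. The change is worth making because it is cheap and the counts cannot be reliably recovered later.

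**What to change.** - In sections 7.4 and 9.2.2, replace the Yes/No item with numeric fields: capsules missed in the past 14 days, capsules missed since the last visit, and the longest run of consecutive missed doses.
- Ask them at the reviews that cover the dosing period. At the twelve-week review only the since-last-visit count and the longest run are informative, because they pick up the capsules due after the six-week review.
- Reconcile 5.2.6 and 7.4 into one adherence definition, including what follows from the label. Which rule should stand is for the investigators to decide.
- Derive adherence from the counts in the analysis, and report the number of doses missed as well as the proportion adherent.
- State whether patient report or the capsule count in 5.2.5 feeds the feasibility measure.

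The cost is two or three numeric entries per review in place of one tick, a small change to the RedCap form, and a few words in the protocol. No extra visit or staff is needed.

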### 9.2.3 Record Retention

Data will be kept for 15 years after the completion of the trial. Hard-copy consent forms will be stored in a locked office in the department of surgery. Electronic data will be stored on a

---

locked laptop using a password protected file. Records will not be destroyed without the written consent of the primary investigator. [name], primary researcher, will have access to the stored data and will be responsible for deleting data at the end of the archival period. Hard-copy consent forms will be shredded.

#### **9.2.3.1 Registration of a Biobank**

Not applicable.

#### **9.2.3.2 Sample Storage and Management**

Not applicable.

### **10 STUDY OVERSIGHT**

#### **10.1 Governance structure**

##### **10.1.1 Trial Management Group (TMG)**

The Site Principal Investigator is responsible for supervising any individual or party to whom they have delegated tasks at the trial site. They must provide continuous supervision and documentation of their oversight. To meet this GCP requirement, a small group will be responsible for the day-to-day management of the trial and will include at a minimum the Site PI and, project coordinator and statistician. The group will closely review all aspects of the conduct and progress of the trial, ensuring that there is a forum for identifying and addressing issues. Meetings must be minuted with attendees listed, pertinent emails retained and phone calls documented.

##### **10.1.2 Trial Steering Committee (TSC)**

A TSC will be established to provide expert advice and overall supervision, and ensure that the trial is conducted to the required standards. The SSC will meet at least annually, with more frequent meetings as needed, and will work to a Terms of Reference.

##### **10.1.3 Safety Monitoring**

Safety oversight will be under the direction of an Independent Safety Monitor, whose primary responsibility is to provide independent safety monitoring in a timely fashion. The Independent Safety Monitor will operate within agreed terms of reference / approved charter and will provide input to the Sponsor-Investigator.

#### **10.2 Site Monitoring**

Trial site monitoring is conducted to ensure that the rights and well-being of trial participants are protected, that the reported trial data are accurate, complete, and verifiable, and that the conduct of the trial is in compliance with the currently approved protocol and amendment(s), good clinical practice and applicable regulatory requirements.

Full details of trial site monitoring are documented in the Clinical Monitoring Plan (CMP). The CMP describes in detail who will conduct the monitoring, at what frequency monitoring will

---

be done, at what level of detail monitoring will be performed, and the distribution of monitoring reports.

Monitoring for this trial will be performed by [name], director of research at Frankston Public hospital. Monitoring will be on-site, occurring yearly, and will review consent forms, assess eligibility data and monitor for safety and withdrawals from treatment.

The investigational site will provide direct access to all trial related sites, source data/documents, and reports for the purpose of monitoring and auditing by the sponsor, and inspection by local and regulatory authorities.

### **10.3 Quality Control and Quality Assurance**

Both the Sponsor-Investigator and Site Investigator have responsibilities in relation to quality management.

The Sponsor-Investigator will develop SOPs that identify, evaluate and control risk for all aspects of the trial, e.g. trial design, source data management, training, eligibility, informed consent and adverse event reporting. The Sponsor-Investigator will also implement quality control (QC) procedures, which will include the data entry system and data QC checks. Any missing data or data anomalies will be communicated to the site(s) for clarification/resolution.

As outlined in the previous section (Site Monitoring), the trial monitors will verify that the clinical trial is conducted and data are generated and biological specimens are collected, documented (recorded), and reported in compliance with the protocol, good clinical practice and applicable regulatory requirements.

In the event of non-compliance that significantly affects human participant protection or reliability of results, the Sponsor-Investigator will perform a root cause analysis and corrective and preventative action plan (CAPA).

In addition, each clinical site will perform internal quality management of trial conduct, data and biological specimen collection, documentation and completion. An individualised quality management plan will be developed to describe a site's quality management.

